## **14.2 Appendix 2: Guidelines for immune-related Response Criteria (irRC) using one-dimensional measurements (simulating RECIST 1.1)**

### **14.2.1 Introduction**

The currently used immune-related response criteria (irRC) uses unidimensional measurements to assess tumor response and it is an adaptation of the original irRC published by Wolchok ([Wolchok et al 2009](#), [Nishino 2013](#)).

The purpose of this document is to summarize the irRC guidelines in details focusing on differences in tumor response assessments between irRC and RECIST v1.1.

The primary difference between irRC and RECIST 1.1 is the definition of progressive disease. The definitions of baseline target/non target lesions, number of lesions selected at baseline, the criteria for lesion measurement method of evaluation of response and definition of response are the same for irRC and RECIST 1.1 and are available in the RECIST 1.1 guidelines ([Appendix 1](#)).

### **14.2.2 New lesions and non-target lesions**

In irRC a new lesion does not automatically indicate progressive disease.

New measurable lesions are added to the sum of diameters of the previously existing target lesions, and the sum of diameters is followed at each subsequent tumor assessment.

New measurable lesions are defined using the same criteria as for baseline target lesions in RECIST v1.1. New measurable lesions shall be prioritized according to size, and the largest lesions shall be selected as new measured lesions up to 10 lesions in total.

Non-target lesions (baseline and new non-measurable lesions) are used primarily for determination of Complete Response (CR). The RECIST v1.1 definitions for the assessment of non-target lesions apply. A CR requires that all non-target lesions disappear (both those present at baseline and any new non-measurable lesions that have appeared during the study). If after worsening a non-target lesion becomes measurable, it should still be followed as a non-target lesion. Worsening of non-target lesions and new non-measurable lesions only indicate disease progression if there is unequivocal evidence of disease progression ([Table 14-6](#)).

### **14.2.3 Follow-up evaluation of target and non-target lesions**

To assess tumor response, the sum of diameters for all target lesions is calculated (at baseline and throughout the study). The diameters of any new measurable lesions are included in the sum of diameters at each assessment to provide the total tumor burden. At each assessment, percent change in the sum of diameters is calculated and compared to baseline or to nadir in order to evaluate the target lesion response (including new measurable lesions) ([Section 14.2.4](#)). This evaluation combined with the status of non-target lesions (baseline and new non-measurable lesions) is then used to determinate the overall lesion response ([Table 14-6](#)). The thresholds for irPR and irPD assessment are the same as for RECIST v1.1.

#### 14.2.4 Definitions of response categories and evaluation of overall lesion response

In irRC, the overall response is primarily based on target lesions (baseline and new measurable lesions). The non-target lesions only contribute to define irCR, and irPD in the case of unequivocal progression, as shown below in [Table 14-6](#).

Like in RECIST 1.1, irCR and irPR must be confirmed at a new assessment after at least 4 weeks. Unlike RECIST 1.1, irPD also requires confirmation at a new assessment after at least 4 weeks.

The response categories are defined as follows:

- **Immune related Complete Response (irCR):** Disappearance of all non-nodal target lesions and non-target lesions in two consecutive observations not less than 4 weeks apart. In addition, any pathological lymph nodes assigned as target lesions must have a reduction in short axis to < 10 mm. (Sum of diameters may be greater than zero at the time of CR, if nodal lesions are included as target lesions).
- **Immune related Partial Response (irPR):** At least a 30% decrease in the sum of diameters of all target lesions including new measurable lesions in two consecutive observations not less than 4 weeks apart, taking as reference the baseline sum of diameters.
- **Immune related Progressive Disease (irPD):** At least a 20% increase in the sum of diameters of all measured target lesions including new measurable lesions. The irPD must be confirmed in a second evaluation not less than 4 weeks later, taking as reference the smallest sum of diameter of all target lesions recorded at or after baseline (nadir). In addition to the relative increase of 20%, the sum must also demonstrate an absolute increase of at least 5 mm. Worsening of non-target lesions (existing or new) only indicate PD when there is unequivocal evidence of progression, confirmed in a second evaluation not less than 4 weeks later.
- **Immune related Stable Disease (irSD):** Neither a sufficient shrinkage to qualify for irPR or irCR, nor an increase in lesions which would qualify for irPD.
- **Unknown (UNK):** Progression has not been documented and one or more target lesions have not been assessed or have been assessed using a method significantly different from baseline that prevents reasonable comparison to the prior assessments.

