#### **7.1.6 Follow up for disease progression**

All patients who discontinue study treatment for any reason other than:

- disease progression per irRC (for patients treated with PDR001)
- disease progression per RECIST v1.1 (for patients treated with chemotherapy)
- clinical deterioration, death, lost to follow up or consent withdrawal

should return for tumor evaluation assessments (please refer to [Table 7-4](#)) until disease progression, death, discontinuation from the study for any other reason (e.g., loss to follow-up or withdrawal of consent), the initiation of a new antineoplastic treatment, or until the End of the Study whichever occurs first.

If patients refuse to return for these visits or are unable to do so, every effort should be made to contact them or a knowledgeable informant by telephone, e-mail or letter, to determine if the patient had disease progression. Once the Follow up for Disease progression period ended, the End of Post treatment Phase disposition eCRF should be completed.

Antineoplastic therapies or tumor directed surgical procedures initiated during the disease progression follow-up period must be recorded on the Antineoplastic therapies since discontinuation of study drug eCRF.

The disease progression follow-up will not be performed for patients who transfer to another study or to an alternative treatment option to continue provision of study treatment.

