#### **10.5.2 Other secondary efficacy objectives**

Efficacy endpoints ORR, BOR and TTP will be also assessed. irPFS will be derived using irRC ([Appendix 2](#)) based on central assessments. An immune related progression disease (irPD) is confirmed by 2 repeated scans at least 4 weeks apart from date of first documented irPD, and the date of 1st scan is defined as the date of irPD.

Individual lesion measurements, overall lesion response, duration of response (DOR), BOR, irPFS and OS will be listed by patient. BOR and ORR will be summarized by treatment arm with accompanying 95% confidence intervals. OS and DOR will be presented descriptively using Kaplan Meier plots. Median OS and DOR will be estimated along with 95% confidence

intervals. The OS rates along with 95% CIs will be provided at 6, 12, 18 and 24 months for each treatment arm using the Kaplan Meier distribution. A stratified Cox regression model will be used to estimate the HR of PDR001 arm vs. the control arm in OS and irPFS, respectively, along with 95% CI for HR.

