### **10.8 Sample size calculation**

Assuming a 2:1 randomization ratio of PDR001 vs. Comparator, 70 events (PD or death) are to be observed in the randomized Phase II to provide 85% power to detect a 0.55 hazard ratio in terms of PFS (corresponding to a median PFS of 10 months in PDR001 group and 5.5 months in the Comparator group), using a log-rank test at a 1-sided significance level of 0.1.

The final primary analysis of PFS will be done using a Bayesian proportional hazard model when there are at least 70 events observed. Based on the simulation results under different scenarios (see [Appendix 3](#)), 70 events provide reasonable operating characteristics in terms of the probability of obtaining a positive result (as defined in [Section 10.4.2](#)). Using the Bayesian

Cox PH model with mixture MAP prior for the yields reasonable 1-sided type I error (0.081) assuming no efficacy (HR=1) and power (0.92) assuming substantial efficacy (HR=0.55) when current data is in alignment with historical data.

Considering a uniform recruitment time of about 14 months and a 15% drop out rate at 12 months, approximately 114 patients need to be randomized in a 2:1 ratio to the two arms in order to observe 70 events after approximately 6 months follow up (approximately 20 months after FPFV):

- 76 patients to the PDR001 arm
- 38 patients to the control arm

EAST® trial design software v5.4 is used to compute the sample size.

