## End dates

The end dates which are used to calculate ‘time to event’ variables are defined as follows:

- Date of death (during treatment as recorded on the treatment completion page or during follow-up as recorded on the study evaluation completion page or the survival follow-up page).
- Date of progression is the first assessment date at which the overall lesion response was recorded as progressive disease.
- Date of last adequate tumor assessment is the date the last tumor assessment with overall lesion response of CR, PR or SD which was made before an event or a censoring reason occurred. In this case the last tumor evaluation date at that assessment is used. If no post-baseline assessments are available (before an event or a censoring reason occurred) the date of randomization/start of treatment is used.
- Date of next scheduled assessment is the date of the last adequate tumor assessment plus the protocol specified time interval for assessments. This date may be used if back-dating is considered when the event occurred beyond the acceptable time window for the next tumor assessment as per protocol (see [Section 14.1.3.2.8](#)).

**Example** (if protocol defined schedule of assessments is 3 months): tumor assessments at baseline - 3 months - 6 months - missing - missing - PD. Date of next scheduled assessment would then correspond to 9 months.

- Date of discontinuation is the date of the end of treatment visit.
- Date of last contact is defined as the last date the patient was known to be alive. This corresponds to the latest date for either the visit date, lab sample date or tumor assessment date. If available, the last known date patient alive from the survival follow-up page is used. If no survival follow-up is available, the date of discontinuation is used as last contact date.
- Date of secondary anti-cancer therapy is defined as the start date of any additional (secondary) antineoplastic therapy or surgery.

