2.7 Analysis of the secondary efficacy variables

Evaluation of anti-tumor activity will be based on central review of overall lesion response according to RECIST v1.1 (see [CPDR01X2201-Protocol-Appendix 1](#)) and irRC ([CPDR01X2201-Protocol-Appendix 2](#)). The variables used to evaluate anti-tumor activity are OS, ORR, BOR, DOR, TTP as per RECIST v1.1 and irPFS as per irRC. Summaries and listings described in this section will be done by study arms based on the FAS.

Individual lesion measurements, overall lesion response, OS, DOR, and irPFS will be listed by patient. OS, ORR, BOR, DOR, TTP and irPFS will be summarized as per specification in [Table 2-3](#). A waterfall plot of best percentage change from baseline in sum of longest diameters of target lesions per RECIST 1.1 and total measured tumor burden (TMTB) per irRC ([CPDR01X2201-Protocol-Appendix 2](#)) will be presented for each study treatment group.

Table 2-3 Analysis of the secondary efficacy variables

Endpoint	Definition	Analysis
----------	------------	----------

OS	Time from the date of randomization to date of death due to any cause. If a patient is not known to have died, survival will be censored at the date of last known date patient alive.	A Kaplan-Meier plot for OS will be presented. Median OS (in months) with corresponding 95% CI, 25th and 75th percentiles (Brookmeyer and Crowley 1982, Klein and Moeschberger 1997) and Kaplan-Meier estimated probabilities (OS rate) with corresponding 95% CIs (Greenwood's formula, Kalbfleisch and Prentice 1980) at several time points (6, 12, 18 and 24 months) will be presented. The number (%) of deaths and patients censored will also be summarized.
irPFS (per irRC)	Time from the date of randomization to the date of the first documented disease progression (irPD) (CPDR01X2201-Protocol-Appendix 2), or death due to any cause.	Median irPFS (in months) with corresponding 95% CI, 25th and 75th percentiles (Brookmeyer and Crowley 1982, Klein and Moeschberger 1997) and Kaplan-Meier estimated probabilities (irPFS rate) with corresponding 95% CIs (Greenwood's formula, Kalbfleisch and Prentice 1980) at several time points (2, 4, 6, 8 and 12 months) will be presented. The number (%) of progressions, deaths and patients censored will also be summarized. The analysis of irPFS will be done for PDR001 arm and crossover patients if there are more than 10 crossover patients.

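### A first irPD that is never re-scanned has no scoring rule, so the PDR001 irPFS estimate may be overstated

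*Protocol*

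**What the plan says.** Three places define the irPFS event.

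- Protocol Section 14.2.4 (Appendix 2): "The irPD must be confirmed in a second evaluation not less than 4 weeks later". Section 7.2.1 and the footnote to Table 14-6 repeat the requirement.
- Protocol Section 10.5.2: an irPD is "confirmed by 2 repeated scans at least 4 weeks apart from date of first documented irPD", and the event is dated at the first scan.
- SAP Section 2.7, Table 2-3: "Time from the date of randomization to the date of the first documented disease progression (irPD", followed by a pointer to Appendix 2, or death from any cause. The OS and TTP rows have a censoring sentence. The irPFS row has none.

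On who keeps being scanned, the plan is to treat and image PDR001 patients until irPD is confirmed (Figure 4-1 note; Section 7.1.2). Section 7.1.6, however, requires no further tumour assessments from patients who stop for reasons including "clinical deterioration, death, lost to follow up or consent withdrawal", and a new antineoplastic treatment also ends them. Section 7.2.1 bases treatment decisions on local reads, while Section 10.5.2 derives irPFS from central reads. Table 7-4 schedules no separate confirmatory scan; the next one is 8 or 12 weeks later.

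On censoring, Appendix 1 (Section 14.1.3.2.7) says: "Date of last adequate tumor assessment is the date the last tumor assessment with overall lesion response of CR, PR or SD". Its Table 14-5 covers PFS, TTP and duration of response and does not name irPFS.

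**The concern.** An irPD that must be confirmed needs a second scan, and the protocol has routes by which a patient can have a first irPD and no second scan. Neither document says what such a patient contributes to irPFS. Under the confirmation rule the irPD is not an event. With Appendix 1's censoring date, the patient's time then stops at the last CR, PR or SD scan, before the progression that was seen. If the patient dies and the death is counted, the event falls later than the irPD.

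Both outcomes lengthen irPFS, and the censoring would be informative, because patients who are deteriorating are the least likely to be re-scanned. SAP Table 2-3 limits irPFS to the PDR001 arm and, if numerous enough, crossover patients, so no control estimate would show the shift. Two programmers could also derive different irPFS from the same data.

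**Working it through.** **Plan's own figure.** The documents give no figure for irPFS. The nearest is the primary PFS design in Section 10.8: "70 events (PD or death) are to be observed in the randomized Phase II to provide 85% power to detect a 0.55 hazard ratio", "using a log-rank test at a 1-sided significance level of 0.1", with 2:1 allocation. Schoenfeld's formula gives (1.282 + 1.036)² / [(2/3)(1/3)(ln 0.55)²] = 5.37 / 0.0794 = 68 events; with 70 events the power is 85.9%. The design reproduces, and this point does not touch it.

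**Inputs for irPFS.**
- Scans every 8 weeks to week 40 (Table 7-4). Eight weeks = 56/30.44 = 1.84 months, so three scans (weeks 8, 16 and 24) fall within 6 months.
- 82 patients randomised to PDR001 (Amendment 06 study status).
- True median 5.5 months, borrowed from the control PFS assumption for illustration; 3 and 10 months as a range.
- Share *f* of first irPDs never re-scanned: not in the documents. Assumption, 10-30%.

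**Formula.** Let *p* be the chance of progression between two scans. With exponential progression and median 5.5 months, p = 1 − 2^(−1.84/5.5) = 0.207. If every first irPD counts, each scan multiplies the Kaplan-Meier curve by 1 − p. If a share *f* is censored at the preceding scan, the risk set at the next scan falls to 1 − fp and the events to p(1 − f), so the factor becomes (1 − p)/(1 − fp). The 6-month rate is that factor cubed.

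| f | factor | 6-month rate | shift (points) |
|---|---|---|---|
| 0 | 0.793 | 0.499 | 0 |
| 10% | 0.793/0.979 = 0.810 | 0.531 | +3.2 |
| 20% | 0.793/0.959 = 0.827 | 0.566 | +6.7 |
| 30% | 0.793/0.938 = 0.846 | 0.605 | +10.6 |

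A Kaplan-Meier simulation on the protocol scan schedule gives the same rates. At f = 20% it also gives +6.7 points for a true median of 3 months (27.9% to 34.6%) and +5.1 for 10 months (68.3% to 73.4%).

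**Deaths.** A death soon after the irPD may still count as an event. Counting deaths within two scan intervals (16 weeks), with an assumed median of 6 months from irPD to death, gives 0.525, 0.553 and 0.582 at f = 10%, 20% and 30%: shifts of 2.6, 5.4 and 8.3 points.

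**Deaths before progression.** Adding a death hazard of 0.01 per month without progression lowers the starting rate to 0.468. The censored rates become 0.498, 0.531 and 0.566 (+3.0, +6.3, +9.8). With deaths before two missed scans counted they are 0.494, 0.520 and 0.549 (+2.6, +5.2, +8.1).

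**Scale.** The standard error of a 6-month rate near 0.47 with 82 patients is √(0.47 × 0.53/82) = 0.055. Kaplan-Meier medians are a poor measure here because they jump between scan dates, so the rates are used.

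**The case against.** **Censoring is nowhere instructed.** Table 14-5 does not name irPFS. Appendix 1 also dates progression at the first assessment recorded as PD, and Table 14-6 assigns irPD at an assessment with confirmation only in a footnote. With the SAP's reference to the first documented irPD, an un-rescanned irPD could be counted at its first date, and then there is no bias. This stands as a permissible reading, but so does the opposite one, because Sections 14.2.4 and 10.5.2 make confirmation part of the definition.

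**The number of such patients is unknown.** A reader might infer that many PDR001 patients leave scanning at their first irPD. The documents do not support that: the plan is to continue to confirmed irPD, stopping for irRC progression read literally means confirmed progression, and no figure is given. What remains is clinical deterioration, new therapy and disagreement between local and central reads.

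**The definitions may not conflict.** The wording in Section 10.5.2 can mean two scans in all, with the first dating the event, which agrees with Appendix 2. It is unclear rather than plainly different.

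**Early deaths do not supply the missing share.** A reader might subtract median PFS (about 5.5 months) from median OS (12-13 months), take about 7 months of post-progression survival, and infer that 1 − exp(−ln 2 × 1.84/7), about 17%, die before the next scan. Those deaths are themselves irPFS events, and a difference of medians from chemotherapy cohorts is not a survival time on PDR001.

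**A rule may exist elsewhere.** The SAP introduction places derived-variable specifications in a separate document, and the independent review charter is not available here. That is possible, but Appendix 1 (Section 14.1.3.2.9) itself asks the protocol and analysis plan to specify event and censoring dates for the primary analysis. A named secondary endpoint needs the same clarity.

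**The consequence is limited.** irPFS has no hypothesis or power, and the SAP reports it descriptively. This stands, and limits the weight of the point.

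**Conclusion.** The point holds in conditional form. The plan makes confirmation part of irPD, allows some PDR001 patients to leave before confirmation, and has no rule for them. If those irPDs are treated as non-events and censored at the preceding scan, or moved to a later death, PDR001 irPFS is overstated. If they are counted at their own date, there is no bias.

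For a true median of 5.5 months and an assumed 10-30% unconfirmed, the 6-month rate is too high by about 3-10 points, or about 3-8 points when deaths before two missed scans count. At 20% that is roughly one standard error. The share, the exponential form and the post-progression survival are assumptions.

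A reader might extend this to the primary result or to the comparison between arms. The documents do not support that: the primary endpoint is central RECIST v1.1 PFS, and although Section 10.5.2 plans an irPFS hazard ratio, the SAP restricts irPFS to PDR001 and crossover patients. The text should be corrected, but the main conclusion of the trial does not depend on it.

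**What to change.** Use one definition in Section 10.5.2, Appendix 2 and the irPFS row of SAP Table 2-3: irPD is confirmed by one further adequate scan at least 4 weeks later, and the event is dated at the first irPD scan.

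For the main irPFS analysis, add that a first irPD is also an event at its own date when no later adequate scan exists because of stopping for progression, clinical deterioration, new therapy or death. It is a non-event only when a later adequate scan fails to confirm it. Give the row an explicit censoring rule for patients with no irPD and no death.

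Add a sensitivity analysis that censors unconfirmed irPDs, including those followed by loss to follow-up, where the missing scan says least about progression. Report the number of unconfirmed irPDs with the reason no later scan exists; this replaces the assumed share with a fact.

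The cost is wording in both documents and one derivation rule, with no new data and no change to patient care. The downside is that a few true pseudo-progressions that were never re-scanned will count as events, which makes irPFS slightly less favourable; the sensitivity analysis shows the other extreme.

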**Table 14-6 Overall response at each assessment**

Target and new measurable lesions (Tumor burden), * (%)	Non-target lesions (both baseline and new non-measurable)	Overall lesion response
- 100	Absent	irCR a
- 100	Stable/not evaluated	irPR a
≤-30	Absent/Stable/not evaluated	irPR a
>-30 and <+20	Absent/Stable/not evaluated	irSD
≥+20	Any	irPD a
Any	Unequivocal progression	irPD a

\*the diameter of new measurable lesions is included in the calculation of the sum of diameters.

a To be confirmed after at least 4 weeks.

If the evaluation of any of the target lesions could not be made during follow-up, the overall status must be ‘unknown’ unless progression was documented.

If the evaluation of any non-target lesions is not made, and all target lesions disappeared, irCR cannot be determined and overall response must be “irPR”.

In some circumstances it may be difficult to distinguish residual disease from normal tissue. When the evaluation of complete response depends on this determination, it is recommended that the residual lesion be investigated (fine needle aspirate/biopsy) to confirm the irCR.

